#### **9.4.3 Safety Analyses**

All safety analyses will be performed on the Safety Population.

All safety data will be listed according to treatment group, subject number, and visit.

The AEs are defined in [Section 8.3.1](#). The DLAE are defined in [Section 4.6](#).

AEs will be coded using the Medical Dictionary for Regulatory Activities (MedDRA) Version 22. The number of AEs and incidence rates will be tabulated by preferred term and system organ class.

The AEs will be coded by maximum severity, relationship to study treatment, as SAEs or DLTs as needed, and will be categorized and tabulated for each treatment group (cohort).

DLAEs will be presented in the same manner as the AEs.

Incidence of injection site reactions will be summarized by treatment group, and if appropriate by assessment time.

All laboratory test results, vital signs measurements, ECG results, weight, and body mass index will be summarized for each treatment group using descriptive statistics at each visit for raw numbers and change from baseline. The incidence of treatment-emergent abnormal laboratory, vital sign, and ECG values will also be summarized using descriptive statistics.

For 12-lead ECG parameters (HR, PR, QRS, QT, QTcF), the 90 % confidence interval will also be presented for each parameter mean and change from baseline values. Outliers for QT and QTcF defined under outcome measures will be summarized using counts and percentages by treatment and sampling time, if appropriate and using subject-level maximum over time by treatment. The following categories will be presented by treatment and overall, for JK07:

- outlier QT and QTcF intervals (450-480 ms, 480-500 ms and >500 ms)
- change from baseline in QT and QTcF intervals (30-60 ms and >60 ms)

Additional corrections to QT may also be similarly analyzed. If relevant, analysis excluding ECGs capturing paced beats will be performed.

Abnormal findings on 12-lead ECG will be summarized by treatment using descriptive statistics.

All recorded ECGs will be interpreted on site and subsequently collected, digitized, and sent for central laboratory standardized measurements. The incidence (number of subjects and percent) of a confirmed positive ADA response will be summarized by treatment. The incidence of neutralizing anti-drug antibody response will also be summarized, if appropriate.

All data will be provided in data listings sorted by treatment group, subject number, and visit.

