### **B. Purpose of the Statistical Analysis Plan**

This Statistical Analysis Plan (SAP) is based on the JK07.1.01 study Protocol Amendment 3.0, providing additional details concerning the statistical analyses outlined in the protocol and reflecting any changes to the protocol.

This SAP will govern the analysis of data from this study. This plan contains definitions of analysis populations, derived variables, data handling rules, format of data presentation and statistical methods for the safety, pharmacokinetic (PK), and pharmacodynamic (PD) analyses. The plan may be modified until the time of database lock. The database will be locked after medical/scientific review of the data has been completed, protocol deviations have been identified, and the data have been declared clean. The purpose of the SAP is to ensure the credibility of the study findings by pre-specified statistical approaches to the study data prior to the database lock. This plan will not repeat all the definitions given in the protocol but will provide further details of summaries and analyses planned therein. Any deviations from the analysis plan, including any after the time of database lock, will be documented as such in the study report. Table, Listing, and Figure (TLF) shells are provided in a separate, accompanying document. The SAP will take precedence over the protocol.

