### **III. Study Endpoints**

#### **A. Primary**

- Incidence and severity of treatment-emergent adverse events (TEAEs) and their relationship to the investigational product (IP).
- 12-lead electrocardiogram (ECG) parameters (heart rate, PR, QRS, QT, QTcF) change from baseline derived as mean from triplicate ECG recording as well as QT and QTcF outlier analyses.
- Change from Baseline in the incidence of rhythm abnormalities (retrieved from telemetry readings for 48 hours postdose).
- Change from Baseline in Laboratory parameters (hematology, chemistry, coagulation, and lipid panels)
- Immunogenicity:
  - Incidence of early and delayed-type hypersensitivity responses
  - Presence of serum anti-JK07 antibodies (confirmed positive antibody response, titer, neutralizing antibodies)
- Change from Baseline in Vital Signs (Blood Pressure, Temperature, Heart Rate, Respiratory Rate)

- Relationship between Vital Signs (Blood Pressure, Temperature, Heart Rate, Respiratory Rate) and JK07, comparing with relationship between Vital Signs and Placebo

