#### **G. Electrocardiograms (Digital 12-Lead Triplicate ECGs)**

Each subject will receive triplicate, twelve-lead ECG evaluations including HR, PR, QRS, QT (uncorrected), QTcF (corrected), and an overall evaluation of normality and clinical significance during screening and starting on Day 1 following admission to the hospital. ECG data will be collected, reviewed and analyzed by a Central Reader and the Principal Investigator. Findings identified by the Central Reader will be listed only for the concerned subjects.

The triplicate measurements of each subject at each timepoint will be averaged before summary. The observed values and mean CFBL of these ECG measurements will be summarized by cohort at each timepoint using descriptive statistics including 90% confidence interval of the mean. The overall ECG evaluation results, alone with shift from baseline (from abnormal to normal, or from normal to abnormal) will be summarized in a separate table by each treatment cohort and aggregated placebo at each visit. Results collected by the Central Reader and the Principal Investigator will be displayed separately.

Categories of QT and QTcF intervals (431-450 ms and >450 ms for males, and 451-470 and >470 ms for females) and CFBL in QT and QTcF intervals (30-60 ms, and >60 ms) will be summarized using counts and percentages by cohort and sampling time. Additional corrections to QT may be analyzed in a similar way. Results collected by the Central Reader and the Principal Investigator will be displayed separately.

A significant proportion of HFrEF patients with pre-existing implanted functional atrio-ventricular (A-V sequential) pacemakers and cardiac resynchronization devices (CRT), may be unevaluable with respect to QT/QTc analysis due to the inherently prolonged and fixed QRS configuration. The presence of these devices, which include defibrillators, is not considered an increased safety risk.

The electrocardiogram analysis will be conducted by cohort in the following two groups and presented separately:

- All subjects
- Subjects not having pacemakers identified by the contents of ECG overall evaluation. If none of the ECG evaluations have the word “pace” or “paced” or “pacemaker” or “electronic” or “electronically” or “resynchronization” or “CRT” for a subject, the subject is considered not to have a pacemaker or CRT (cardiac resynchronization therapy).

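### SAP VII.G replaces the protocol's 450-480, 480-500 and >500 ms QT/QTcF categories with open-topped >450/>470 ms ones, undeclared, so no summary it specifies counts subjects who ever exceeded 480 or 500 ms

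*SAP*

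**What the plan says.** Both documents make the outlier analysis part of a primary safety endpoint. The SAP's endpoint list gives ECG changes from baseline "as well as QT and QTcF outlier analyses", and Protocol Table 3 agrees.

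Protocol 9.4.3 sets the method. It introduces the categories with "The following categories will be presented by treatment and overall, for JK07", and the absolute ones are "outlier QT and QTcF intervals (450-480 ms, 480-500 ms and >500 ms", the same for both sexes. Counts are to be made by treatment and sampling time if appropriate, and also "using subject-level maximum over time by treatment".

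SAP VII.G specifies something else: "Categories of QT and QTcF intervals (431-450 ms and >450 ms for males, and 451-470 and >470 ms for females". These "will be summarized using counts and percentages by cohort and sampling time". It mentions no subject-level maximum and no pooled JK07 presentation of these rows. The change-from-baseline categories (30-60 and >60 ms) are the same in both documents.

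On precedence, SAP I.B states: "The SAP will take precedence over the protocol". The SAP's Changes from Protocol section covers only the dropped summary of abnormal vital signs.

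**The concern.** The SAP's top categories have no upper limit, so they merge a value just over the eligibility limit with one well above 500 ms. The cut-points of 450 ms (males) and 470 ms (females) are those of exclusion criterion 12, which may be where they came from, but the SAP gives no reason. A limit that screens subjects in does not grade how far QTcF moves after dosing.

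The protocol treats the higher values as important in their own right. Its dose-limiting adverse event (DLAE) guidance in section 4.6 names QTcF above 500 ms and a rise above 60 ms from baseline as separate triggers. The SAP's summary keeps only the second as a category. A reader of the final report would want the number of subjects who ever crossed 480 or 500 ms, by dose group and against placebo, and the SAP text does not produce it.

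**Working it through.** **Inputs.** Protocol categories and counting rule: Protocol 9.4.3. SAP categories and counting rule: SAP VII.G. Eligibility limits (QTcF above 450 ms in males or 470 ms in females excludes): Protocol 5.2, criterion 12. The plan gives no figure to reproduce, so the check is whether the protocol's counts can be recovered from the SAP's.

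**Step 1: map values to rows.**

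| QTcF (ms) | Protocol | SAP, male | SAP, female |
|---|---|---|---|
| 455 | 450-480 | >450 | 451-470 |
| 475 | 450-480 | >450 | >470 |
| 485 | 480-500 | >450 | >470 |
| 505 | >500 | >450 | >470 |
| 540 | >500 | >450 | >470 |

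For males, the single row >450 takes in all three protocol categories. For females, 450-480 is split between 451-470 and >470, and >470 also absorbs 480-500 and >500. No protocol category can be recovered exactly, and counts above 480 or 500 ms cannot be recovered for either sex.

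**Step 2: do the change rows fill the gap?** Only in part.

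- A value above 500 ms with a rise of 60 ms or less needs a baseline above 500 - 60 = 440 ms. Within the criterion 12 limits that is above 440 to 450 ms in males and above 440 to 470 ms in females.
- A value above 480 ms with a rise below 30 ms needs a baseline above 480 - 30 = 450 ms. Within the limits that is females only, above 450 to 470 ms.

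Illustrative cases:

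| Sex | Baseline | Post-dose | Rise | Protocol row | SAP absolute row | SAP change row |
|---|---|---|---|---|---|---|
| M | 450 | 505 | 55 | >500 | >450 | 30-60 |
| M | 420 | 455 | 35 | 450-480 | >450 | 30-60 |
| F | 465 | 505 | 40 | >500 | >470 | 30-60 |
| F | 440 | 475 | 35 | 450-480 | >470 | 30-60 |
| F | 465 | 490 | 25 | 480-500 | >470 | none |
| M | 450 | 512 | 62 | >500 | >450 | >60 |

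The first two males are tabulated identically under the SAP, as are the first two females. The third female passes 480 ms and enters no change row. The last male shows where the change rows do help: at 512 ms, any baseline of 450 ms or less gives a rise of at least 62 ms.

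**Step 3: counting unit.** Suppose one flag appears at each of three sampling times. The table shows 1, 1, 1 whether that is one subject flagged three times or three subjects flagged once each. The number of subjects ever above a threshold therefore cannot be obtained by adding the counts by time point. This is what the protocol's subject-level maximum provides.

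**Step 4: other specified outputs.** The descriptive maximum at each time point shows that at least one subject crossed a threshold, not how many. The by-subject ECG listing and the QT/QTcF category listing show values, but give no count with a denominator. DLAE tables depend on the Data Review Committee's discretion and are tabulated by system organ class and preferred term. They do not address 480 ms.

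**The case against.** The strongest reply has four parts.

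- **The endpoint sets no cut-point.** It asks only for outlier analyses. The 450/480/500 ms categories and the subject-level maximum appear in Protocol 9.4.3 alone; the synopsis has neither. This stands. The departure is from the protocol's stated method, not from the endpoint's wording. But 9.4.3 commits to those categories, and the SAP drops them without saying so.
- **The table shells were not available.** SAP I.B says the "shells are provided in a separate, accompanying document", and they might contain the protocol's rows. This limits the finding to the SAP text. If the shells do contain them, they contradict the governing text, which still needs correcting.
- **Adverse event tables count subjects.** A clinically significant ECG abnormality is to be recorded as an adverse event, and those tables count each subject once. That is true, but recording rests on the investigator's judgement, so it is not a count above a fixed threshold.
- **The loss is small.** Cohorts have 5 to 9 subjects, the study has at most 63, analyses are descriptive, and one subject can be told from three in the listings. This stands as a limit on severity. Hand-counting from listings is still not a pre-specified summary, and it would have to be repeated for each display that VII.G requires.

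The missing pooled JK07 column is the weakest part: SAP V.M's general provision for overall results where appropriate may cover it.

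**Conclusion.** The concern holds and should be fixed. The SAP replaces the protocol's absolute QT/QTcF categories, does not declare the change, and states no subject-level maximum. Its summary therefore cannot report how many subjects ever exceeded 480 or 500 ms. The consequence falls on the final report: no data are lost, and nothing here shows an effect on dose-escalation decisions, for which the SAP refers data reports to the committee's charter.

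The mapping in Step 1 and the counting point in Step 3 need no assumption beyond the two texts. The baseline ranges in Step 2 assume that Day 1 baseline QTcF is within the criterion 12 limits, and the individual cases are illustrative. The conclusion does not depend on group size or on whether sentinel subjects are in the Safety Evaluation Population.

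**What to change.** In SAP VII.G:

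- Add the protocol's absolute categories as inequalities: >450 to <=480, >480 to <=500 and >500 ms. The protocol's own ranges share the value 480. This wording also leaves exactly 450 ms outside the lowest category, which the SAP should state.
- Keep the sex-specific rows if wanted, and leave the 30-60 and >60 ms change categories as they are.
- Report counts and percentages by dose group, pooled JK07 and pooled placebo in two ways: (a) at each sampling time, as now; (b) by each subject's maximum post-dose triplicate mean, with subjects having at least one post-dose ECG as denominator. State whether unscheduled ECGs enter the maximum.
- List any remaining departure from Protocol 9.4.3 in Changes from Protocol, with the reason.

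Declaring the change without restoring the categories would cure the omission, but would still leave no count above 480 or 500 ms.

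The cost is SAP wording and one or two table shells, with no new data. VII.G already asks for Central Reader and Principal Investigator results separately, and for all subjects and those without pacemakers separately, so each shell may be run in up to 2 x 2 = 4 versions.

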### 1.3 Schedule of Activities

**Table 1 Schedule of Assessments**

(note that X denotes activity on a given day, but may denote a single or multiple instances of the indicated activity)

	Screening	In Hospital		Follow-up										EOS/ 180 t	
		Subjects must be fasted for 10 hours before each on-site visit													
Study Day	-45 to 0	1 a	2	3	4	7	11 v	15	22 v	30	60	90	135		
Window						+1	-1	+/-2	+/-2	+/-2	+/-5	+/-5	+/-7	+/-10	
In-patient stay a		X	X	X											
Hospital discharge b					X										
Informed consent	X														
Demographics	X														
Past medical history	X														
Height (at screening only) and Weight	X	X		X		X	X	X		X	X	X	X	X	
Vital signs (at same time point as ECGs)	X	X	X	X	X	X	X v	X		X	X	X	X	X	
Physical examination c	X	X	X	X	X	X	X v	X	X v	X	X	X	X	X	
Blood-based pregnancy test d	X														
Urine pregnancy test d		X								X	X	X	X	X	
IP administration		X													
Check for injection site reaction e		X	X	X	X										
Adverse events f		X	X	X	X	X	X	X	X	X	X	X	X	X	
Review concomitant medications	X	X	X	X	X	X	X	X	X	X	X	X	X	X	
Serum chemistry and liver, kidney, and coagulation panels g	X	X	X			X		X		X	X g	X g	X g	X	
Complete blood count h	X	X	X	X		X		X		X	X	X	X	X	

	Screening	In Hospital		Follow-up										EOS/ 180 t
		Subjects must be fasted for 10 hours before each on-site visit												
Study Day	-45 to 0	1 a	2	3	4	7	11 v	15	22 v	30	60	90	135	
Window						+1	-1	+/-2	+/-2	+/-2	+/-5	+/-5	+/-7	+/-10
Lipid panel i	X	X	X			X		X		X	X	X	X	X
Urinalysis j	X	X	X			X		X						
Muscle and inflammatory biomarkers k		X	X			X		X		X	X	X	X	X
Additional biomarkers: Cardiac troponins, CPK-MB, CPK, and hsCRP assessment l	X	X	X	X		X		X		X	X	X	X	X
Immunogenicity Assessment m		X			X	X		X		X		X		X
Telemetry n		X	X	X										
Digital 12-lead ECG o	X	X	X	X	X	X	X v	X		X	X	X	X	X
2D-TTE p	X	X	X			X		X		X	X	X	X	X
PK sample collection q		X	X	X	X	X	X v	X	X v	X	X			
Fingerstick glucose r		X	X	X	X									
ECG patch recording s	X													
Thyroid panel	X													
Viral serology	X													

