- The post-screening times for the ECGs will be as follows: prior to the IP infusion, immediately following IP infusion, 0.5, 1, 2, 4, and 8 hours from the end of the IP infusion, 24- and 48-hours clock-time matched within  $\pm$  30 minutes of pre-dose Day 1 ECG assessment, prior to a light breakfast/snack (see [Table 2](#) for additional details).
- These ECGs will be read by the Investigator to ensure subject safety. These ECGs must be taken immediately before PK sampling.

p On Day 1, 2D-TTE measurements will be performed pre-dose and at  $6 \pm 0.5$  hours post-dose. On Day 2, the assessment is scheduled for  $30 \pm 0.5$  hours post-dose.

See [Section 8.2.9](#) for a description of exploratory 2D-TTE assessments.

q The PK blood samples will be collected as follows: Prior to the IP administration, at the end of the infusion, at 0.5, 1, 2, 4, 8, and 12 hours, at 24 hours (Day 2) and 48 hours (Day 3) timed to no more than 10 minutes following completion of ECG assessment, at 72 hours (Day 4), 144 hours (Day 7), 240 hours (Day 11), 336 hours (Day 15), and 504 hours (Day 22) from the end of the infusion, and on Day 30 and Day 60 (see [Table 2](#)). Note that sample collection times may be modified based on emerging PK results and 1 additional blood sample may be collected if deemed appropriate (up to 18 samples). Windows for the first 48 hours of PK collections are identified in [Table 2](#); a  $\pm 8$ -hour window is permitted for PK collections on Day 4 and a  $+1$  day is permitted on Day 7. Windows for subsequent PK sample collections are indicated in the SoA above.

r Blood glucose samples will be collected by fingerprick test and read using standard glucometer at the same timepoint as the PK samples through 96h (Day 4) postdose. HbA1c to be performed at the Screening visit only.

s During the screening period and no more than 45 days before Day 1, all subjects will be supplied with, and instructed how to use a e-Patch for continuous 14-day heart rhythm monitoring. Subjects must then perform 14 continuous days of heart rhythm monitoring using the e-Patch. Unless otherwise approved by the sponsor, monitoring should be completed no later than Day -10 to allow for processing of data by the manufacturer and evaluation of baseline ECG parameters and arrhythmia incidents by the site.

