### **XIII. Changes from Protocol**

Per Protocol section 9.4.3 Safety Analyses, the incidence of treatment-emergent abnormal vital signs should be summarized using descriptive statistics. However, no abnormality flag for vital signs was collected, therefore no specific table or listing for abnormal vital signs will be produced.

Note that abnormal and clinically significant vital signs will be registered as adverse events, as mentioned in the Protocol section 8.3.7: “Any emergent laboratory abnormality (e.g., clinical chemistry or hematology) or other abnormal assessment findings (e.g., ECG or vital signs) that meets any of the following criteria should be recorded as an AE or SAE”.

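### The SAP's no-pacemaker ECG group rests on a word search that misses 'pacing' and matches negated text, and the exploratory C-QT model has no rule for paced ECGs

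*SAP*

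**What the plan says.** **Safety ECG tables.** SAP VII.G presents the ECG analysis by cohort twice: for all subjects, and for "Subjects not having pacemakers identified by the contents of ECG overall evaluation". The rule for the second group opens "If none of the ECG evaluations have the word" and gives seven alternatives: pace, paced, pacemaker, electronic, electronically, resynchronization, CRT. A subject with no hit in any evaluation counts as having no device. The stated reason is that patients with pacemakers or resynchronisation devices "may be unevaluable with respect to QT/QTc analysis due to the inherently prolonged and fixed QRS configuration". The by-subject ECG listing is also to show whether each subject has a pacing device, but that item does not form the group.

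**Protocol rule.** Protocol 9.4.3 says: "If relevant, analysis excluding ECGs capturing paced beats will be performed". The SAP's Changes from Protocol section deals only with vital signs ("no specific table or listing for abnormal vital signs will be produced").

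**Pacing at entry.** Under Protocol 5.1, criterion 5, a subject with an ICD may enter with up to 15% paced beats if a non-paced Day 1 baseline ECG can be obtained. Protocol 8.2.5 requires the screening and Day 1 baseline ECGs to be free of pacing. Nothing comparable is said of post-dose ECGs.

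**C-QT model.** SAP IX.B and Protocol 9.4.2 (Exploratory Exposure-Response Analysis) model change from baseline in QTcF on time-matched concentration. SAP IX.B.4 compares the upper 90% bound with 10 ms. Neither section mentions pacing.

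**The concern.** QT and QTcF change and outliers belong to a primary endpoint. The second set of tables exists so that a reader can see the ECG results without device patients. If a word search decides membership, the tables are only as sound as the match between those seven words and the vocabulary of whoever wrote the evaluations. The protocol itself uses 'pacing' for this finding (8.2.5), and that word is not on the list.

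In the C-QT model, an unpaced baseline subtracted from a paced post-dose ECG puts any pacing artefact straight into the change score. The VII.G grouping is not carried into IX.B, so no planned output would show how much such records influence the estimate.

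**Working it through.** **1. The word search.** The seven terms were run on invented phrases, ignoring case, as substrings and as whole words. The SAP does not say which applies.

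| Phrase | Substring | Whole word |
|---|---|---|
| ventricular pacing; biventricular pacing; AV sequential pacing; atrial pacing | no hit | no hit |
| ventricular paced rhythm | hit | hit |
| no pacemaker; not paced; no CRT | hit | hit |
| unpaced rhythm | hit | no hit |

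'Pace' is not contained in 'pacing', hence the first row. The third row shows negated text removing a subject.

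**2. How many evaluations can trigger removal.** In Table 1 of the protocol, the row "Digital 12-lead ECG" with footnote o gives:
- screening: 1;
- Day 1: 7 ("prior to the IP infusion, immediately following IP infusion, 0.5, 1, 2, 4, and 8 hours from the end of the IP infusion");
- 24 h and 48 h: 2;
- Days 4, 7, 11, 15, 30, 60, 90, 135 and 180: 9.

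Total 1 + 7 + 2 + 9 = 19, or 18 if Day 11 is remote. One hit at any of these removes the subject from the second group at all of them. Conversely, a paced subject stays in only if no evaluation contains a listed word.

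**3. Cost of wrongly dropping one unpaced active subject.** Active subjects per cohort, counting the sentinel (an assumption): 1 + 3 = 4 in a basic cohort and 1 + 6 = 7 in an expanded one (Protocol 4.2). The 90% CI half-width in SD units is t(0.95, n-1)/√n.
- n = 4: 2.353/√4 = 1.177; n = 3: 2.920/√3 = 1.686; ratio 1.43.
- n = 7: 1.943/√7 = 0.734; n = 6: 2.015/√6 = 0.823; ratio 1.12.

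This needs no assumption about artefact size, only equal SD.

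**4. C-QT illustration.** The documents give neither the size nor the frequency of a pacing artefact; 30 and 60 ms are assumed. SAP IX.B.4 estimates ΔΔQTc(C) = θ1 + C·θ2. The shift from one record is its generalised-least-squares weight in that estimate times the artefact.

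Further assumptions:
- the SAP's fixed effects without the baseline covariate;
- the five planned doses, with dose-proportional concentrations declining mono-exponentially;
- half-life 12-72 h;
- subject SD 5-8 ms, residual SD 8 ms, random slope SD 0-5 ms at top-dose Cmax;
- eight paired post-dose times: end of infusion, 0.5, 1, 2, 4, 8, 24 and 48 h.

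Records: 5 × 5 × 8 = 200 (basic cohorts) or 5 × 9 × 8 = 360 (expanded).

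| One fully paced record, 30 ms artefact | Basic | Expanded |
|---|---|---|
| Top-dose subject, end of infusion | +1.0 to +1.75 ms | +0.6 to +1.0 ms |
| Placebo subject, end of infusion | -0.9 to -1.4 ms | -0.4 to -0.7 ms |

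A 60 ms artefact doubles each figure. At 48 h a placebo record in basic cohorts gives about -0.4 to +0.5 ms, so its direction is not fixed.

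The eight-time set is a choice. Protocol 9.4.2 refers to Day 1 concentrations, which leaves six post-dose pairs. SAP IX.B.4 drops that limit, and Table 1 would allow up to 14.

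**5. Which exclusions reach the C-QT data.** Protocol 9.4.2 uses the exploratory PD/biomarker population. Protocol Table 11 lets that population exclude for deviations or events judged to affect PD results. SAP V.K keeps only major protocol deviations. A paced ECG in an eligible ICD subject is not a deviation, so under the SAP no stated exclusion covers it.

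**The case against.** The strongest reply is that the SAP group is based on devices, not on tracings. Its rationale is the fixed QRS of device patients, so removing whole subjects is the design. Wherever the search works, it removes every paced ECG and is stricter than the protocol's exclusion, which is itself conditional. This stands in part: subject-level removal is not an error in itself. But an ICD subject can have both paced and unpaced ECGs, so the two exclusions answer different questions, and the SAP does not record the substitution.

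Several protections also exist. The all-subjects tables are kept. Central-reader and investigator results are shown separately. The listing lets a reader check device status. Exclusion criterion 11 removes some abnormal ECGs at screening. The C-QT model runs only if the exploratory plots support its assumptions; otherwise a separate modelling plan is required. All analyses are exploratory and descriptive, so the 10 ms comparison is not a formal test. These points limit the consequence. They do not correct a misclassified table or show the effect of paced records on the C-QT estimate.

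A reader might infer that subjects will in fact be misclassified. The documents do not support that: they give no evaluation text, and every phrase tested above was invented.

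A reader might also count the missing rule for a triplicate with only some tracings paced as a defect of the same rank, since "The triplicate measurements of each subject at each timepoint will be averaged before summary". It is missing detail. The documents do not show that pacing is recorded per tracing, so such a rule may not be workable.

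**Conclusion.** The point holds as a flaw in a stated rule and a gap in a planned analysis. As written, the search can put subjects in the wrong group in either direction. The change from the protocol's ECG-level exclusion is undeclared. The C-QT model has no paced-ECG exclusion or sensitivity analysis.

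The firmest figure is the loss of precision if one unpaced active subject is dropped: 43% or 12%, conditional on that happening. The C-QT shifts rest on an assumed artefact and the model settings above. They show that a single record could move the estimate by an amount worth knowing against a 10 ms threshold. They do not show that the comparison with 10 ms would change, nor that bias would run in one direction, and neither should be inferred.

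This should be corrected before database lock. It does not undermine the all-subjects safety tables.

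**What to change.** 1. Add 'pacing' to the terms in SAP VII.G. Before database lock, check both hits and non-hits against the device status to be listed and the central-reader findings. Staff doing this should be blinded wherever the cohort is still blinded (sentinels are open-label, and Protocol 6.3 permits earlier cohorts to be unblinded).
2. Beside the existing tables, add the record-level QT/QTcF analysis without paced ECGs that Protocol 9.4.3 describes.
3. If the C-QT model is run, repeat it without paced ECG records as a sensitivity analysis. Report the number excluded by treatment, because post-dose pacing may itself be an outcome.
4. List any remaining difference under Changes from Protocol.

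Cost: wording in SAP VII.G, IX.B and Changes from Protocol; one extra model run; and a manual review of ECG comments to mark paced records, since no per-ECG pacing flag is documented. An unknown number of ECG records would be lost from the unpaced analysis.
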